# 4.4 Planned Sample Size and Number of Study Centers

It is planned to recruit 1000 patients at approximately 80 sites in the USA and EU for this study. See Section 8.8 for a discussion of sample size.

# 4.5 Patient Identification and Randomization

# 4.5.1 Patient Identification

At the screening visit, a unique 6-digit patient number will be assigned consecutively for each patient after he or she signs the ICF. Unique patient numbers will begin with the clinical site number, e.g., 001 followed by a 3 digit number starting with 001. The unique patient numbers will be assigned sequentially. For example, for clinical site number 002, the unique patient numbers will be as follows: 002-001, 002-002, 002-003. The patient will keep this unique patient number for the duration of the study.

Patients who drop out of the study before randomization will retain their unique patient number (i.e., the patient number will not be reassigned). If a patient is rescreened after being designated as a screen failure, the patient will receive a new unique patient number upon rescreening.

# 4.5.2 Randomization Scheme

No randomization will be performed. All patients will be assigned into active treatment with SI-6603.

# 4.5.3 Allocation/Randomization of Patients to Treatment

Not applicable.

# 5 STUDY DRUG

For details and handling of the investigational drug (SI-6603), refer to the IB and Appendix 11.1, Injection Procedure, and Investigational Drug Management Procedure.

# 5.1 Identity

SI-6603 will be administered as a lyophilized injection which, when reconstituted with 1.2 mL of saline, provides 1.0 mL containing the ingredients given below.

Ingredient					
Active ingredient	Condoliase				
	Monosodium phosphate dihydrate (United States Pharmacopoeia				
	[USP])				
	Sodium dihydrogen phosphate dehydrate (European				
	Pharmacopoeia[EP])				
Inactive ingredients	Disodium hydrogen phosphate, dodecahydrate (USP)				
-	Disodium phosphate dodecahydrate (EP)				
	Sucrose (National Formulary [NF], EP)				
	Polyethylene glycol 3350 (NF)				
	Macrogol 3350 (EP)				

SI-6603 for injection (1.25 U [1.5 U/vial]) will be manufactured for reconstitution with the 1.2 mL of saline for delivery of 1.25 U in 1.0 mL.

#### 5.2 Administration

An SI-6603 for injection vial will be reconstituted with 1.2 mL of saline to prepare a 1.25 U/mL solution of SI-6603. A volume of 1.0 mL will be administered into the intervertebral disc in a single-dose (see Appendix 11.1).

# 5.3 Packaging, Labeling and Storage

SI-6603 will be packaged by the vendor according to all local legal requirements. SI-6603 will be labeled in accordance with applicable regulatory requirements (see Appendix 11.2, Package Presentation and Labeling).

All SI-6603 supplies must be stored in the original boxes in accordance with the manufacturer's instructions (2 to 8°C and shielded from light). SI-6603 must be stored in a securely locked area, accessible to authorized personnel only.

# 5.4 Blinding and Breaking the Blind

The study is not blinded.

# 5.5 Drug Accountability

The Investigator is responsible for maintaining accurate SI-6603 accountability records throughout the study. Each dispensing of SI-6603 must be documented in the patient source record and eCRF. The Investigator is responsible for returning all unused or partially used SI-6603 to the Sponsor and must verify that no remaining supplies are in the Investigator's possession.

# 5.6 Compliance

Compliance with the injection procedure is to be monitored and recorded by site staff. Study treatment consists of the investigational drug administered on Day 0 (a single intradiscal injection of SI 6603).

# 5.7 Previous and Concomitant Medications

Any medication the patient takes other than the investigational drug, including herbal and other nontraditional remedies, is considered a concomitant medication. All concomitant medications must be recorded in the patient source record and eCRF for each concomitant medication as follows: generic name (for combination drug only, trade name must be recorded), route of administration, start date, stop date, dosage, and indication. Any changes in the dosage or regimen of a concomitant medication must be recorded in the patient source record and eCRF.

Previous and concomitant medication data will be captured beginning at the time of informed consent. At screening, patients will be asked what medications they have taken during the last 6 weeks. At each subsequent study visit, patients will be asked what concomitant medications they are currently taking or have taken since the last visit.

# 5.7.1 Permitted Concomitant Medication

Concomitant medications used in the treatment of lumbar disc herniation and complications associated with disc herniation are allowed. There is no restriction on concomitant medications used in treatment of diseases or disorders other than lumbar disc herniation.

# 5.7.2 Notes Concerning Concomitant Medication Before SI-6603 is Administered

SI-6603 is a foreign protein preparation of *Proteus vulgaris* and may have the potential to cause an allergic reaction. The concomitant use of drugs that are contraindicated during the use of epinephrine may interfere with the effect of the epinephrine, which is used for treatment in the early stage of anaphylactic reaction. Therefore, other alternatives should be considered for treatment of anaphylactic reaction for patients using the following classes of drugs:

- Contraindicated drug of epinephrine (e.g., antipsychotic drug or α-blocker)
- β-blocker

Intradiscal injection procedure itself has risk of bleeding and/or infection at the injection site. Patients continuously being treated with anticoagulants and/or immunosuppressants should be taken to in account for an extra caution before receiving intradiscal injection, according to following instructions:

- During the assessment of patient eligibility in screening visit and before performing the intradiscal injection, review patient medical records to assure there are no concomitant use of anticoagulants and/or immunosuppressants.
- If concomitant use of anticoagulants and/or immunosuppressants are recognized, investigators should assess whether such patients are eligible to go through intradiscal injection procedure.

# 5.8 **Previous and Concomitant Therapies**

Any therapy the patient uses in the treatment of lumbar disc herniation is considered a concomitant therapy. All concomitant therapies must be recorded in the patient source record and eCRF. The following information must be recorded in the patient source record and eCRF for each concomitant therapy: therapy name, frequency, start date, stop date. Any changes in the frequency and administration method of a concomitant medication must be record and eCRF.

Previous and concomitant therapy data will be captured beginning at the time of informed consent. At screening, patients will be asked what therapies they have used during the last 6 weeks. At each subsequent study visit, patients will be asked what concomitant therapies they are currently taking or have taken since the last visit.

#### 5.8.1 Permitted Concomitant Therapies

The conservative therapies used in the treatment of lumbar disc herniation prior to the time of informed consent are allowed. There is no restriction on therapies used in treatment of diseases or disorders other than lumbar disc herniation.

#### 5.8.2 Prohibited Concomitant Therapies

Lumbar operation, lumbar percutaneous nucleotomy, or lumbar intradiscal therapies (e.g., chemonucleolysis, intradiscal electrothermal treatment) for treatment of back pain and leg pain are prohibited from the time of informed consent up to the final observation (Week 26 after investigational drug administration). A patient who requires lumbar operation, lumbar percutaneous nucleotomy, or lumbar intradiscal therapies (e.g., chemonucleolysis or intradiscal electrothermal treatment) in the clinical study period must be discontinued from the clinical study.

In addition, discography for diagnostic purpose is also prohibited from the time of informed consent through Week 13 after investigational drug administration.

#### **6 VARIABLES AND METHODS OF ASSESSMENT**

#### 6.1 Safety Variables

#### 6.1.1 Adverse Events

All AEs will be coded using Medical Dictionary for Regulatory Activities (MedDRA) terminology (Section 9.4).

#### 6.1.1.1 Collection of Adverse Events

It is the responsibility of the Investigator to collect all AEs (both serious and non-serious) derived by spontaneous, unsolicited reports of patients, by observation and by routine open questionings e.g., "How have you felt since I last saw you?"

#### 6.1.1.2 Definitions

An AE is any untoward medical occurrence that occurs in a patient or clinical investigation subject administered a pharmaceutical product, and which does not necessarily have a causal relationship with this treatment. An AE can therefore be any unfavorable and unintended sign (including abnormal laboratory finding), symptom, or disease temporally associated with the use of an investigational product, whether or not considered related to the product.

For this study, the following imaging findings will be recorded as AEs:

- Disc height (disc index): decrease in disc height ≥30% compared to baseline value
- Vertebral posterior angle: vertebral body angle formed by flexion of  $\geq 5^{\circ}$
- Vertebral body translation: vertebral body translation of  $\geq 3 \text{ mm}$
- Change in vertebral body endplates and adjacent bone marrow: Type 1, Type 2, or Type 3 change (Modic Classification)

Note: The above events are limited to the targeted level of the procedure and the adjacent vertebral bodies.

All AEs, including intercurrent illnesses, occurring during the study will be documented in the eCRF. Concomitant illnesses, which existed before entry into the study, will not be considered AEs unless they worsen during the treatment period. All AEs, regardless of the source of identification (e.g., physical examination, laboratory assessment, or reported by patient), must be documented.

Pre-existing conditions will be recorded in the eCRF on the Medical History or appropriate page.

A treatment-emergent adverse event will be defined as an AE that begins or that worsens in severity after the study drug has been administered.

#### 6.1.1.3 Assessment of Adverse Events

Each AE will be assessed by the Investigator with regard to the following categories.

#### 6.1.1.3.1 Seriousness

A SAE is defined as any untoward medical occurrence that at any dose:

- Results in death
- Is life-threatening This means that the patient is at risk of death at the time of the event; it does not mean that the event hypothetically might have caused death if it were more severe.
- Requires inpatient hospitalization or prolongation of existing hospitalization
- Results in persistent or significant disability or incapacity
- Is a congenital anomaly or birth defect
- Is an important medical event(s) that may not be immediately life-threatening or result in death or hospitalization but that may jeopardize the patient or require intervention to prevent one of the above outcomes. Examples of such events are intensive treatment in an emergency room or at home for allergic bronchospasm; blood dyscrasias or convulsions that do not result in hospitalization; or development of drug dependency or drug abuse.

Medical and scientific judgment should be exercised in deciding whether a case is serious and whether expedited reporting is appropriate.

#### 6.1.1.3.2 Intensity

The intensity of each AE must be assessed by the Investigator using one of the following categories, and recorded in the eCRF:

- Mild: No particular interference with the patient's activities of daily living (ADL) or, despite slight interference, no particular intervention indicated; Common Terminology Criteria for Adverse Events (CTCAE) Grade 1 (see Appendix 11.8)
- Moderate: Interference with the patient's ADL and minimal intervention indicated; CTCAE Grade 2
- Severe: Disabling and almost complete interference with the patient's ADL or systemic intervention indicated; CTCAE Grade 3/4

#### 6.1.1.3.3 Causality

The Investigator will assess the causality / relationship between the study drug and the AE and record that assessment in the eCRF. Causality will be shown as related or not related.

The most likely cause of an SAE (e.g., disease under treatment, concomitant disease, concomitant medication, other) will be indicated on the eCRF with details of the concomitant disease or medication or other cause.

The causal relationship of the AE to the study drug will be described in terms of:

• Not related: There is no temporal correlation or attributability to the investigational medicinal product, but to any other factor, such as the underlying disease, a complication, a concomitant drug, a predisposition, or concomitant intervention, by which the AE can be explicitly explained.

• Related: There is a reasonable possibility that the relevant event can be judged to be at least due to the investigational drug or a causal relationship cannot be ruled out.

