#### 1.3.1.6 Intradiscal Injection

Due to the procedure itself, temporary discomfort, injection-site pain, bleeding, vascular damage, bruising vagal reaction, nerve damage, disc damage and/or infection at the injection site may occur.

Adverse event	SI-660	03 Group (N			Placebo Group (N=128)				
SOC/PT		AE Subjects (%)		Drug related AE Subjects (%)		AE ects (%)		related E ets (%)	
Infections and infestations							5		
Nasopharyngitis	41	(15.2)			14	(10.9)			
Influenza	5	(1.9)			2	(1.6)			
Pharyngitis	3	(1.1)			1	(0.8)			
Gingivitis	3	(1.1)			1	(0.8)			
Tonsillitis	2	(0.7)			1	(0.8)			
Mastitis	1	(0.4)							
Otitis media	1	(0.4)							
Periodontitis	1	(0.4)			1	(0.8)			
Hordeolum	1	(0.4)							
Bronchitis	1	(0.4)		,		;			
Rhinitis	1	(0.4)			1	(0.8)			
Urinary tract infection	1	(0.4)							
Oral herpes					1	(0.8)			
Gastroenteritis					1	(0.8)			
Infected dermal cyst					1	(0.8)			
Neoplasms benign, malignant and unspecified	(including cys	ts and poly	os)			. /			
Uterine leiomyoma	$\frac{1}{2}$	(0.7)							
Blood and lymphatic system disorders		~ /							
Lymphadenitis	1	(0.4)	1	(0.4)		;			
Immune system disorders		()		()					
Allergy to arthropod sting					1	(0.8)			
Metabolism and nutrition disorders						(0.0)			
Hyperlipidaemia	2	(0.7)							
Dyslipidaemia	$-\frac{2}{1}$	(0.4)							
Hyperkalaemia		(0.4)			1	(0.8)	1	(0.8	
Psychiatric disorders					1	(0.0)	1	(0.0	
Insomnia	2	(0.7)							
Panic disorder	1	(0.4)							
Anxiety disorder	1	(0.4)							
Nervous system disorders		()							
Hypoaesthesia	8	(3.0)	1	(0.4)	7	(5.5)	1	(0.8	
Headache	6	(2.2)	3	(1.1)	5	(3.9)		,0.0	
Dizziness	3	(1.1)		()	1	(0.8)			
Sensory disturbance	2	(0.7)	1	(0.4)	1	(0.8)			
Dysaesthesia	1	(0.4)		(0.4)		(0.0)			
Lumbar radiculopathy	1	(0.4)	-	(0.1)	1	(0.8)			
Cervicobrachial syndrome	1	(0.4)			1	(0.0)			
Migraine	1	(0.4)							
Convulsion	1	(0.7)			1	(0.8)			
Hyporeflexia					1	(0.8)			
Presyncope					2	(1.6)			
Radial nerve palsy					1	(1.0) (0.8)			

Adverse event	SI-660	03 Group (1	N=269)	Placebo Group (N=128)				
SOC/PT	AE Subjects (%)		Drug related AE Subjects (%)		AE Subjects (%)		Drug related AE Subjects (%)	
Sciatica					1	(0.8)	~	(, , )
Somnolence					1	(0.8)		
Tremor					1	(0.8)		
Piriformis syndrome					1	(0.8)		
Vagus nerve disorder					1	(0.8)	1	(0.8)
Eye disorders								
Conjunctivitis allergic	1	(0.4)						
Dry eye	1	(0.4)						
Ear and labyrinth disorders								
Vertigo positional	1	(0.4)						
Cardiac disorders								
Arrhythmia	1	(0.4)						

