#### Clinical Study Protocol CONFIDENTIAL

Adverse event	SI-6603 Group (N=269)					Placebo Group (N=128)			
SOC/PT		AE Subjects (%)		Drug related AE Subjects (%)		AE Subjects (%)		Drug related AE Subjects (%)	
Skin and subcutaneous tissue disorders							5	~ /	
Dermatitis contact	7	(2.6)			1	(0.8)			
Rash	6	(2.2)	4	(1.5)	1	(0.8)			
Pruritus	2	(0.7)	2	(0.7)					
Urticaria	2	(0.7)	2	(0.7)					
Toxic skin eruption	2	(0.7)	1	(0.4)					
Blister	1	(0.4)	1	(0.4)					
Drug eruption	1	(0.4)	1	(0.4)					
Skin warm	1	(0.4)	1	(0.4)					
Erythema	1	(0.4)							
Eczema	1	(0.4)			2	(1.6)			
Alopecia	1	(0.4)							
Musculoskeletal and connective tissue disorders									
Back pain	95	(35.3)	64	(23.8)	42	(32.8)	6	(4.7	
Pain in extremity	46	(17.1)	11	(4.1)	35	(27.3)	3	(2.3	
Myalgia	7	(2.6)							
Arthralgia	3	(1.1)							
Osteoarthritis	3	(1.1)							
Musculoskeletal pain	2	(0.7)	1	(0.4)	2	(1.6)	1	(0.8	
Intervertebral disc protrusion	2	(0.7)			8	(6.3)			
Periarthritis	1	(0.4)			1	(0.8)			
Arthritis	1	(0.4)							
Tendonitis	1	(0.4)							
Myofascial pain syndrome	1	(0.4)							
Muscular weakness	1	(0.4)			2	(1.6)	1	(0.8	
Neck pain	1	(0.4)	1	(0.4)	2	(1.6)			
Muscle fatigue	1	(0.4)	1	(0.4)					
Limb discomfort	1	(0.4)	1	(0.4)	1	(0.8)			
Muscle spasms					1	(0.8)			
Muscle tightness					1	(0.8)			
Renal and urinary disorders									
Haematuria					1	(0.8)			
Reproductive system and breast disorders									
Cervical polyp	1	(0.4)							
Prostatitis					1	(0.8)			
General disorders and administration site conditions									
Injection site pain	33	(12.3)			10	(7.8)			
Pyrexia	5	(1.9)	4	(1.5)	7	(5.5)	4	(3.1	
Chills	1	(0.4)							
Injection site discomfort	1	(0.4)							
Feeling hot	1	(0.4)		;		;			
Vessel puncture site pain					1	(0.8)			

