#### **2** STUDY OBJECTIVES

#### 2.1 Primary Objective

The primary study objective is to evaluate the safety of a single-dose intervertebral disc injection of SI-6603 at a dose of 1.25 U in patients with lumbar disc herniation, for a 26-week follow-up period.

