#### 6.1.1.5 Reporting Serious Adverse Events

All SAEs that occur during the period of observation, and all SAEs occurring up to 26 weeks after receiving the dose of study drug, whether considered to be associated with the study drug or not, must be reported within 24 hours by fax, email or telephone to the PAREXEL Safety Contact using the numbers, and specific mailbox in the List of Study Personnel.

Any SAE occurring after the end of the study should be reported to the Sponsor/PAREXEL by the Investigator if the Investigator considers there is a causal relationship with the study drug.

[figure not shown]
The minimum information required for an initial report is:

- Name of person sending the report (i.e., name, address of Investigator)
- Patient identification (screening/randomization number, initials, NOT patient name)
- Protocol number
- Description of SAE
- Causality assessment, if possible.

However, as far as possible all points on the SAE form should be covered in the initial report, or the completed SAE form itself must be faxed to the PAREXEL Safety Contact. In addition, the event must be documented in the eCRF.

In case the PAREXEL Safety Contact cannot be contacted (e.g., out of normal working hours or at weekends), SAE reports will be received by PAREXEL. The required information should be faxed, emailed or a message should be left on the voicemail service (for phone/fax/email, see the contacts in the List of Study Personnel).

After receipt of the initial report, the safety center will review the information and, if necessary, contact the Investigator, to obtain further information for assessment of the event. PAREXEL will be responsible for all information processing and reporting according to local legal requirements. Where necessary, Investigators will inform Regulatory Authorities in their own countries.

Details for the reporting of Suspected Unexpected Serious Adverse Reactions (SUSARs) can be found in Section 6.1.1.7.

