# 6.1.1.6 Follow-up of Adverse Events

During the study, all AEs experienced by a patient, irrespective of the suspected causality, will be monitored until the AE has resolved, any abnormal laboratory values have returned to baseline or stabilized at a level acceptable to the Investigator and Medical Monitor, until there is a satisfactory explanation for the changes observed, until the patient is lost to follow-up, or until the patient has died. If the AEs are ongoing at the time of the last study visit, only treatment-related AEs will be followed beyond 26 weeks after investigational drug administration until the AE has resolved, any abnormal laboratory values have returned to baseline or stabilized at a level acceptable to the Investigator and Medical Monitor, or until there is a satisfactory explanation for the changes observed. Follow-up of the AEs beyond the entire study duration will be evaluated on case-by-case basis by the Medical Monitor and the Sponsor.

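### Causality is judged only against the study drug, so an AE put down to the puncture alone can be classed as not related and leave three treatment-related rules

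*Combined protocol and SAP*

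**What the plan says.** - **Objective (2.1).** The primary aim is "to evaluate the safety of a single-dose intervertebral disc injection of SI-6603 at a dose of 1.25 U".
- **Known procedure risk (1.3.1.6).** As effects of the procedure itself, the protocol warns that temporary discomfort and "injection-site pain, bleeding, vascular damage, bruising vagal reaction, nerve damage, disc damage and/or infection at the injection site may occur".
- **Causality (6.1.1.3.3).** "The Investigator will assess the causality / relationship between the study drug and the AE and record that assessment in the eCRF". The answer is binary. *Related* includes any event for which a causal link to the drug cannot be excluded. *Not related* requires the absence of a temporal link or attribution to the product, together with another factor. The examples of such a factor include "a concomitant drug, a predisposition, or concomitant intervention, by which the AE can be explicitly explained". A most-likely-cause entry exists for SAEs only, and its examples do not include the injection procedure.
- **AE report content (6.1.1.4).** The listed items include the relationship to study drug. None concerns the procedure.
- **Rules that use the answer.** Section 8.6.1 defines treatment-related AEs, and repeats the SAE analyses, by the related label. For AEs still ongoing at the last visit, section 6.1.1.6 says that "only treatment-related AEs will be followed beyond 26 weeks after investigational drug administration until the AE has resolved", stabilised or been explained. An SAE after the end of the study is to be reported "if the Investigator considers there is a causal relationship with the study drug" (6.1.1.5).
- **DSMB notification (9.10).** The triggering events are listed without a causality condition, but the sentence on notifying the DSMB then calls them treatment-related.

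**The concern.** The drug cannot reach the disc without the needle, so the harm of the treatment under test is the harm of drug and puncture together. The protocol recognises the puncture as a source of harm but gives the investigator nowhere to record it as a cause. A site that is convinced a nerve injury or disc infection came from the needle can reasonably answer *not related* to a question about the drug.

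The trial has one arm and no sham or placebo injection (3.3, 4.5.2). No between-group comparison can later separate procedure harm from drug harm, so investigator attribution is the only tool. Section 8.8 justifies the 1000 patients by the wish to characterise infrequent treatment-related AEs, and that is the quantity this gap can lower. An injury judged procedural and still present at Week 26 would also have no required follow-up under the protocol.

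**Working it through.** **1. The plan's own precision figures.** Section 8.8 uses Clopper-Pearson 95% intervals with n = 1000. The lower limit is the 0.025 quantile of Beta(x, n − x + 1). The upper limit is the 0.975 quantile of Beta(x + 1, n − x).
- x = 3: 0.3% (0.06% to 0.87%).
- x = 15: 1.5% (0.84% to 2.46%).

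Both match the plan. No stated figure is in dispute, and the point rests on definitions.

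**2. Path of an AE judged to be caused by the puncture alone.**

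| Rule | Depends on the drug-related label? | Outcome if *not related* |
|---|---|---|
| AE recording (6.1.1.4) | No | Recorded |
| Overall AE and SAE incidence (8.6.1) | No | Counted |
| SAE report within 24 hours, to Week 26 (6.1.1.5) | No | Reported |
| Treatment-related AE and SAE tables (8.6.1) | Yes | Omitted |
| Follow-up beyond Week 26 (6.1.1.4, 6.1.1.6) | Yes | Not required; case-by-case evaluation only |
| SAE report after study end (6.1.1.5) | Yes | Not required |
| DSMB notification (9.10) | Unclear | The two wordings conflict |

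**3. Effect on the treatment-related rate (illustration).** Assume that 15 of 1000 patients have an event due to drug or procedure, and that m of these are classed as procedure only. The documents give no value for m. The reported rate is (15 − m)/1000, with the interval from step 1.
- m = 0: 1.5% (0.84% to 2.46%)
- m = 3: 1.2% (0.62% to 2.09%)
- m = 5: 1.0% (0.48% to 1.83%)
- m = 10: 0.5% (0.16% to 1.16%)
- m = 15: 0% (0% to 0.37%)

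The overall AE incidence is the same for every m.

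**4. Evidence from earlier studies (Table 1).** For the row "Injection site pain":
- SI-6603: 33/269 = 12.3% (exact 95% CI 8.6% to 16.8%), drug-related cell blank.
- Placebo: 10/128 = 7.8%, drug-related cell blank.

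Reading a blank as zero is an assumption, because the table prints no zeros. If the SI-6603 rate and that labelling carried over, 1000 × 33/269 ≈ 123 patients (86 to 168) would have this AE outside the treatment-related count.

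Table 1 also has contrary rows. Placebo patients received an intradiscal injection without the drug (1.1.2.5, 1.1.2.7). Some of their events were nevertheless classed as drug-related: back pain in 6/128 (4.7%) and vagus nerve disorder in 1/128 (0.8%). A vagal reaction is one of the procedure risks named in 1.3.1.6.

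**5. Follow-up beyond Week 26.** The documents give no rate for persistent procedure injury. At an assumed 0.1% to 0.5%, the count is 0.001 × 1000 = 1 to 0.005 × 1000 = 5 patients. This is a ceiling at those rates, because each event must also be classed as procedure only and still be ongoing at Week 26.

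**The case against.** A reader might infer that all harm from the injection is classed as *not related*. The documents do not support that. Drug and puncture come through the same needle in the same session (11.1.3), so an early injury has a temporal link to the drug. Any event whose link to the drug cannot be excluded is *related*. Section 1.3.1.3, in discussing treatment-related back pain, itself names the injected volume as a possible cause. The protocol never says that the study injection counts as a concomitant intervention. Section 5.6 describes study treatment as the single intradiscal injection. Only harm attributed with confidence to the puncture alone can leave the related category.

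Table 1 pools earlier studies and several doses, and their causality definitions are not in the documents. It cannot show how the present definition will work, and its contrary rows point the other way.

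The safeguards are real. All AEs are recorded and tabulated, SAEs to Week 26 are reported whatever the cause, and 6.1.1.6 leaves follow-up beyond the study to case-by-case evaluation by the medical monitor and the sponsor. The final eCRF, the detailed SAP and the DSMB charter are not available here and might contain more.

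All of this stands, and it narrows the point. It does not remove it. No safeguard identifies procedure causality for a non-serious AE, and none requires follow-up of a procedural injury beyond Week 26. The mixed sorting in Table 1 is itself a reason to ask the question separately.

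**Conclusion.** The gap is real but limited. An AE that the investigator considers fully explained by the puncture can be classed as *not related*. It then drops out of the treatment-related AE and SAE tables, required follow-up beyond Week 26 and post-study SAE reporting. It does not drop out of the overall safety analysis or of SAE reporting to Week 26.

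The size is unknown. The 123 per 1000 is an illustration that rests on one preferred term, on other protocols and on reading blanks as zero. It concerns the incidence tables only. A reader might take it as the number losing follow-up, but the documents give no duration for that pain. A reader might also infer that procedure events are kept from the DSMB. Section 9.10 does not establish this: its list carries no causality condition and its next sentence implies one, so the finding there is a conflict to reconcile.

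The change is worth making because it is cheap and because a single-arm trial has no other way to attribute procedure harm.

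**What to change.** 1. In 6.1.1.3.3, in the AE report content of 6.1.1.4 and on the AE eCRF page, add for every AE: *related to the intradiscal injection procedure (yes/no)*. Keep the existing drug item.
2. In 8.6.1 and the SAP, tabulate drug-related, procedure-related and either. The drug-only rate is kept, so comparison with earlier studies is not lost.
3. Base follow-up beyond Week 26 (3.1, 6.1.1.4, 6.1.1.6) and the post-study SAE sentence in 6.1.1.5 on either.
4. In 9.10, reconcile the list of triggers with the sentence that calls them treatment-related, and align the DSMB charter.

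The cost is one eCRF field, a few protocol sentences and extra columns in the AE tables. The either rate will be somewhat higher than the drug-only rate, and a few more AEs will be followed after Week 26.
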